## Can the fluctuation observed in the endotracheal tube with compression applied to the epigastric region be used as a confirmation method for endotracheal intubation?

### STUDY PROTOCOL

This study was planned prospectively in the emergency department of a tertiary hospital. Ethics committee approval was obtained from the ethics committee of Düzce University (Date: 18/01/2021, Decision no: 2021/05). The relatives of the participants included in the study were informed about the procedure and written informed consent was obtained. The procedure does not pose any additional risk to the routine procedure and the question "Can the tube position be confirmed by epigastric manual compression method in addition to the currently used confirmation methods?" was sought.

#### *Participants*

Patients admitted to the emergency department between 01/05/2021 and 30/05/2022, who were older than 18 years of age and who underwent ETE outside the hospital or within the first hour of arrival to the emergency department were included in the study. Patients in whom ETE was previously confirmed by USG or PETCO2, in whom elective intubation was decided, who were referred from another center, and who had known airway stenosis were excluded from the study. In the literature, it has been shown that >80% of ETE applications in the first attempt are successful [10,11]. This rate is 70% for out-of-hospital cardiac arrest cases [5]. In our clinic, an average of 300 ETE procedures are performed annually and the success rate is similar. Therefore, in order to include an equal number of successful and unsuccessful ETE procedures, the first 40 successful and the first 40 unsuccessful ETE procedures were included in the study. One participant from each group was excluded due to missing data.

#### *Workflow*

Patients who underwent ETE outside the hospital or in the first hour of arrival to the emergency department were evaluated after the procedure. Out-of-hospital ETE was performed by experienced paramedics working in the emergency ambulance service, and ETE in the emergency department was performed by emergency medicine residents or emergency medicine specialists with at least 2 years of emergency department experience. Out-of-

hospital procedures were performed at the first visit to the emergency department, and procedures performed in the emergency department were confirmed by ETE immediately after the procedure.

### ***Statistical analysis***

Descriptive statistics were presented as numbers and percentages. Demographic data were presented as mean±standard deviation (SD) for normally distributed variables and median, IQR (25-75%) for non-normally distributed variables. Pearson's chi-square test and Fisher's exact test (when the expected number of cells was less than five) were used for independent categorical variables. Bonferroni correction was used for subgroup analyses and  $p<0.016$  was considered significant. Sensitivity, specificity, positive likelihood ratio, negative likelihood ratio, positive predictive value and negative predictive value were calculated at 95% CI for the index tests of gastric compression fluctuation, epigastric sound and lung sounds based on the reference test of ultrasound confirmation. Statistical analyses were performed using IBM Corp. Released 2017. IBM SPSS Statistics for Windows, Version 25.0. Armonk, NY: IBM Corp. A P value less than 0.05 was considered statistically significant.

Confirmation was performed single-blind by emergency medicine specialists with at least 5 years of experience, without knowing who performed the procedure and where (in or out of the hospital). Confirmation was performed by auscultation of lung sounds (from the anterior and lateral sides of both lungs, upper and lower zones), evaluation of equal participation of both thoraxes in breathing by inspection, auscultation of the epigastric region, placement of capnography, monitoring of water vapor in the tube, manual compression of the epigastric region at least three times and evaluation of fluctuation in the tube, and pulse oximetry monitoring.

Epigastric compression was performed by applying pressure to the epigastric region at least three times with the volar side of the intubated patient while the patient was ventilated with a balloon-valved mask. During this procedure, the fluctuation of the air and fluid in the stomach inside the esophageal tube can be observed and its sound can be heard. It can be applied from the first inhalation.

The USG procedure was evaluated by placing a linear ultrasound probe [SonoSite M-Turbo linear probe (13-6 MHz), Sonosite, Inc, Bothell, WA, USA] in the transverse position on the anterior side of the neck, just above the suprasternal notch, and observing the position of the tube (presence of a double path sign) and pleural sliding movement. While a single semicircular echogenic area is observed when the tube is in the trachea, a second semicircular echogenic area is observed when the tube is located in the esophagus.. USG was performed immediately after the ETE procedure. In patients in whom double pathway sign was observed and pleural sliding motion was not observed, the patient was re-intubated by the experienced specialist performing USG. It was confirmed by USG again. These procedures were categorized as "failed".

ETCO2 measurement by capnography was performed using a mainstream EMMA® Capnograph (PHASEIN AB Svärdevägen, Danderyd, Sweden) for intubated patients. It was assessed by the detection of PETCO2 greater than 5 mmHg after five breaths and the appearance of a typical square waveform.

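### PPV and NPV are planned on a sample fixed at 50% failed intubations, with no prevalence adjustment, while the protocol's own success figures imply 30% failures or fewer

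*Combined protocol and SAP*

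**What the plan says.** The Participants section fills two quotas: "the first 40 successful and the first 40 unsuccessful ETE procedures were included in the study". Equal group sizes are the stated aim, and one participant per group was then dropped for missing data, so 39 and 39 are analysed.

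The ultrasound description states how a procedure is classed as failed: "In patients in whom double pathway sign was observed and pleural sliding motion was not observed", the tube was replaced and the procedure counted as a failure. The Statistical analysis section (printed twice with the same content) computes accuracy "based on the reference test of ultrasound confirmation". The test that sorts patients into the two quotas is thus also the reference test.

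For each of the three index tests that section plans sensitivity, specificity, both likelihood ratios and both predictive values: "positive predictive value and negative predictive value were calculated at 95% CI". No prevalence, weighting, Bayes step or caveat appears there or elsewhere.

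The only information on how often intubation fails is in the Participants section: "it has been shown that >80% of ETE applications in the first attempt are successful"; "This rate is 70% for out-of-hospital cardiac arrest cases"; and "In our clinic, an average of 300 ETE procedures are performed annually and the success rate is similar".

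**The concern.** A predictive value depends on the test's accuracy and on the share of affected patients among those tested. When the investigator fixes that share by quota, the predictive value read from the table is partly a product of the quota: 40 failed and 80 successful procedures would give different PPVs and NPVs for the same test. Sensitivity, specificity and likelihood ratios condition on the reference result, so the ratio of the groups does not fix them.

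The study asks whether compression can confirm where the tube lies. Of the planned measures, PPV and NPV look most like a direct bedside answer to that. If the true failed share is below 50% and the test is imperfect, the 39/39 table overstates how far an esophageal result (fluctuation seen) can be believed and understates how far a tracheal result (no fluctuation) can be believed. The confidence intervals are centred on the same wrong values. Epigastric and lung sounds are affected likewise.

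A related gap is that the plan never says which result counts as positive for each index test. A reader therefore cannot tell which predictive value will be called PPV.

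**Working it through.** **Inputs from the documents**
- Sample: 40 failed and 40 successful; 39 and 39 analysed.
- Success above 80% gives failure below 20%; success of 70% gives failure of 30%; the clinic is described as similar.
- Volume: about 300 procedures a year.

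**Inputs assumed, because the documents do not give them**
- Sensitivity (se) and specificity (sp) for esophageal placement, set equal at 0.80, 0.90, 0.95 and 0.99.
- Failed share when the tube is checked (p): 30%, 20% and 10%. The 10% value is compatible with success above 80% but is not a figure in the documents.

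**Step 1: the design share.** 40/80 = 39/78 = 50% failed.

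**Step 2: is 50% a natural case mix?** At 30% failures, 78 consecutive procedures would hold about 78 × 0.30 = 23 failures; at 20%, about 78 × 0.20 = 16. The binomial probability of 39 or more is 0.00017 at 30% and about 3 × 10⁻⁹ at 20%. Reaching 40 failures takes about 40/0.30 = 133 procedures (93 successes, of which 40 are kept) or 40/0.20 = 200 procedures (160 successes, of which 40 are kept). The surplus successes are left out of the table.

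**Step 3: predictive values by Bayes' rule**

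Esophageal result: PV = se·p / [se·p + (1 − sp)(1 − p)]

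Tracheal result: PV = sp(1 − p) / [sp(1 − p) + (1 − se)p]

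For example, with se = sp = 0.90 and p = 0.20, the esophageal value is 0.18/(0.18 + 0.08) = 69.2% and the tracheal value is 0.72/(0.72 + 0.02) = 97.3%.

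| se = sp | Result | 50% (design) | 30% | 20% | 10% |
|---|---|---|---|---|---|
| 0.80 | esophageal | 80.0 | 63.2 | 50.0 | 30.8 |
| 0.80 | tracheal | 80.0 | 90.3 | 94.1 | 97.3 |
| 0.90 | esophageal | 90.0 | 79.4 | 69.2 | 50.0 |
| 0.90 | tracheal | 90.0 | 95.5 | 97.3 | 98.8 |
| 0.95 | esophageal | 95.0 | 89.1 | 82.6 | 67.9 |
| 0.95 | tracheal | 95.0 | 97.8 | 98.7 | 99.4 |
| 0.99 | esophageal | 99.0 | 97.7 | 96.1 | 91.7 |
| 0.99 | tracheal | 99.0 | 99.6 | 99.7 | 99.9 |

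**Step 4: the confidence intervals.** Take an invented table with 35/39 correct in each group (se = sp = 0.897). Read directly, the predictive value of an esophageal result is 35/39 = 89.7%, Wilson 95% CI 76.4 to 95.9.

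On the logit scale the variance is (1 − se)/(39·se) + sp/[39(1 − sp)] = 0.0029 + 0.2244 = 0.2273, so the standard error is 0.477. The results are:

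| Failed share | Esophageal result, % (95% CI) | Tracheal result, % (95% CI) |
|---|---|---|
| 50% | 89.7 (77.5–95.7) | 89.7 (77.5–95.7) |
| 30% | 78.9 (59.6–90.5) | 95.3 (88.9–98.1) |
| 20% | 68.6 (46.2–84.8) | 97.2 (93.2–98.9) |
| 10% | 49.3 (27.6–71.2) | 98.7 (96.9–99.5) |

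For the esophageal result, the 30% estimate lies inside the table's Wilson interval; the 20% and 10% estimates lie below it. With 38/39 correct in each group, the esophageal values are 94.2% at 30% and 90.5% at 20%, both inside that table's Wilson interval (86.8 to 99.5).

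**The case against.** The strongest reply is that this touches two of six planned measures. Sensitivity, specificity and both likelihood ratios are already planned with intervals, no passage makes PPV or NPV primary, and likelihood ratios are the standard tool for moving to another prevalence. That is true and makes the repair easy. It does not make the raw PPV and NPV valid, and they will be reported with 95% CIs as if they were.

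Second, for confirming a tracheal tube the error is cautious: the value of a tracheal result is understated. This stands. The value of an esophageal result is overstated at the same time, and by more.

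Third, the size is conditional. The documents give neither accuracy nor the share of esophageal tubes at the check. The cited rates concern intubation success, largely at first attempt, while patients "were evaluated after the procedure". Tubes already confirmed by ultrasound or capnography are excluded, which may shift the share further. The 35/39 example is invented, and a more accurate test shows a smaller effect. All of this limits what can be said about size. It does not rescue 50%, which the quota imposes whatever the true share is and which no figure in the documents supports.

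Fourth, the logit variance is undefined when a group is 39/39 correct, and a within-group bootstrap then shows no variation in that group. This is correct, and the fix below allows for it.

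**Conclusion.** The concern holds. As written, the plan yields predictive values set by a 50% quota, against implied failure rates of 30% or below 20%. With accuracy between 0.80 and 0.95, moving from 50% to 30% failures lowers the predictive value of an esophageal result by about 6 to 17 points, and moving to 20% lowers it by about 12 to 30 points. The value of a tracheal result rises by about 3 to 10 points and 4 to 14 points respectively. At accuracy 0.99 the esophageal value falls by only about 1 to 3 points at these rates, and at 100% accuracy there is no distortion.

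These sizes rest on assumed, equal sensitivity and specificity and on intubation failure as a proxy for the esophageal share at the check. That the problem exists rests only on the sampling scheme and the absence of any adjustment. It should be corrected before the predictive values are reported. It does not invalidate the sensitivity, specificity or likelihood ratios.

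**What to change.** - Do not present PPV and NPV from the 39/39 table as clinical predictive values. If they are shown, label them as valid only at the designed 50% share, and say in the analysis section that this share was set by design.
- State for each index test whether the positive result means esophageal or tracheal placement.
- Derive predictive values by Bayes' rule from the estimated sensitivity and specificity, or the likelihood ratios, over failure rates stated as assumptions, for example 10%, 20% and 30%.
- Give intervals on the logit scale or by bootstrap within each outcome group. State in advance what is done if a group is 39/39 correct: a continuity correction, or exact limits for sensitivity and specificity carried through Bayes' rule.
- If records show how many eligible tubes had been checked by ultrasound when the 40th failure was reached, add that observed share as a scenario.
- Keep sensitivity, specificity and likelihood ratios as the main results.

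The cost is SAP wording and a few lines of calculation, with no new data. Unless accuracy is perfect, at these rates the reported value of an esophageal result will fall and that of a tracheal result will rise.

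### The single-blind rule hides only who intubated and where; nothing masks the fluctuation reading and the ultrasound reference from each other or sets their order, so review bias is permitted

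*Combined protocol and SAP*

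**What the plan says.** The confirmation procedure sits inside the first Statistical analysis section. It is assigned to emergency medicine specialists with at least 5 years of experience, who work "without knowing who performed the procedure and where (in or out of the hospital"). This is the only masking statement in the documents.

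The same paragraph lists what the confirming specialist does, including auscultation, capnography and epigastric compression. USG is not on that list. It is described in separate text after the compression paragraph, which says that "USG was performed immediately after the ETE procedure" and that in failed cases "the patient was re-intubated by the experienced specialist performing USG".

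On timing, the Workflow section states that "procedures performed in the emergency department were confirmed by ETE immediately after the procedure", and that out-of-hospital intubations were assessed at the first visit to the emergency department. Of compression, the plan says "It can be applied from the first inhalation".

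Both Statistical analysis sections name USG as the reference test, and fluctuation, epigastric sound and lung sounds as the index tests.

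**The concern.** In a diagnostic accuracy study, the masking that matters most is between the index test and the reference test. Not knowing who intubated, or where, protects against expectations about skill and setting. It does not stop a reader from interpreting an ambiguous sign in the light of a reference result already known.

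The fluctuation sign involves judgement: the plan says that "the fluctuation of the air and fluid in the stomach inside the esophageal tube can be observed and its sound can be heard". If its reader already knew the USG result, doubtful readings would tend to be settled in agreement with USG, and accuracy would be overstated. If the USG reader already knew the fluctuation reading, the reference label could itself be affected. Since failed procedures are identified by USG, membership of the two groups could then change too.

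The planned 95% confidence intervals describe sampling error only. They would not reveal either effect, and analysts cannot repair it afterwards.

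**Working it through.** There is no stated figure to reproduce: the plan gives no expected sensitivity or specificity and no power calculation. The check is mainly one of text.

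**Step 1. What would be needed, and what is stated.**

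| Element | What the documents say |
|---|---|
| Fluctuation reader masked to USG | Not stated; the rule covers operator and place |
| USG reader masked to fluctuation | Not stated |
| Different people for the two tests | Not stated; separate descriptions only |
| Order of the two readings | Not stated |

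**Step 2. Does any other statement settle the order?**
- Workflow places emergency-department confirmation immediately after the procedure, and the USG text places USG immediately after intubation. Neither is placed before the other.
- The remark about the first inhalation says when compression is possible, not when it was done or recorded.
- Re-intubation of failed cases implies that fluctuation in the original tube was read before that tube was replaced. It does not imply that it was read before the USG result was known.
- The Participants section excludes patients whose tube had previously been confirmed by USG or PETCO2. This removes results obtained before the study assessment, not the study USG itself.

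**Step 3. Scale.**
Inputs from Participants: 40 successful and 40 unsuccessful procedures, one excluded from each group, so 40 − 1 = 39 per group. Taking these groups as the USG-defined classes, they are the denominators of sensitivity and specificity.

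- One swayed fluctuation reading: 1/39 = 2.6 points.
- Two: 2/39 = 5.1 points. Four: 4/39 = 10.3 points.

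With purely assumed counts and exact (Clopper-Pearson) 95% intervals:

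| Count | Estimate | 95% CI |
|---|---|---|
| 35/39 | 89.7% | 75.8–97.1% |
| 37/39 | 94.9% | 82.7–99.4% |
| 39/39 | 100% | 91.0–100% |

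**Step 4. An assumed range.**
Let *p* be the true sensitivity or specificity, and *r* the share of discordant fluctuation readings pulled towards USG. Apparent value = *p* + *r*(1 − *p*), so overstatement = *r*(1 − *p*). Neither *p* nor *r* is in the documents. For *p* from 70% to 95%:
- *r* = 10%: 0.10 × 30 = 3 points down to 0.10 × 5 = 0.5 points.
- *r* = 25%: 7.5 down to 1.25 points.
- *r* = 50%: 15 down to 2.5 points.

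At an assumed *p* of 80% with 39 patients, the exact 95% interval covers the true value 97.5%, 97.4%, 94.4% and 76.2% of the time at *r* = 0, 10%, 25% and 50%. A weak pull therefore does little harm to coverage; a strong one does.

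This model describes only a fluctuation reader drawn towards USG. It does not represent a USG reader drawn towards fluctuation, because the groups of 39 would then no longer be fixed.

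**The case against.** The strongest reply is that this is a silence in a short summary written in the past tense, not a demonstrated defect. The text also leans somewhat towards separate roles: USG is left out of the confirming specialist's list, and the person performing it is mentioned separately. Compression was possible from the first breath, so it could have come before USG. Recruitment dates are closed, so a new recording rule cannot change the existing data. The scale figures rest on assumptions, and weak influence leaves the intervals nearly nominal.

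Much of this stands, and it limits the conclusion. Three stronger readings are tempting but unsupported:
- **That readers were unmasked, or that one person did both tests.** Nothing says so. Equally, a second reader at the same bedside is not masked unless the plan provides for it.
- **That the two readings were simultaneous.** Two uses of the same loose timing phrase show only that no order is given. The Workflow statement also covers only emergency-department cases.
- **That masking to every other test is required.** The stated question is whether compression helps "in addition to the currently used confirmation methods", so knowing auscultation may be part of the intended use. For capnography, which is not the reference, the direction of any effect is unknown.

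The reply does not remove the core point. The plan does state a blinding rule, and that rule leaves out the comparison on which the accuracy results rest.

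**Conclusion.** The point holds as a gap in the blinding rule. Following the rule exactly as written would still allow the fluctuation reading and the USG reference to influence each other. The omission is certain from the text; whether bias occurred is not known.

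The direction can be stated only conditionally. If the fluctuation reader knew the USG result, accuracy would tend to be overstated. If the USG reader knew the fluctuation reading, the reference label and group membership could change as well.

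The only size that follows from the documents is 2.6 points per swayed index reading, with 39 per group. Any total depends on an assumed number of swayed readings. The gap should be fixed because it touches the main accuracy estimates and costs little to close or disclose.

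**What to change.** **For any future recording**, define blinding by test result. Suggested wording: *The fluctuation, epigastric-sound and lung-sound readings are each written down before their reader knows the USG result. The reader and the order of readings are noted. Usual care is never delayed; any reading made after the USG result is known is flagged as unmasked. Where existing staff allow, the USG reader does not know the index readings.*

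The cost is protocol wording and form entries for reader, order and an unmasked flag, with no extra staff or procedure. The downside is a set recording order and some flagged readings, since USG follows intubation immediately.

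**For the data already collected**, report who read each test, in what order and with what knowledge of the other results, and do not let the term single-blind suggest masking to USG unless that took place. If order was recorded, add a sensitivity analysis limited to patients whose fluctuation was read before USG. It has two limits:
- Intervals widen. As an illustration at about 80% observed, 31/39 gives 63.5–90.7% and 16/20 gives 56.3–94.3%.
- The subset may be selected, because reading order could depend on urgency or suspected misplacement.

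If order was not recorded, state as a limitation that the accuracy estimates may be overestimated.

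### The index sign has no fixed number of compressions, no positivity rule and no described masking to the other signs or ultrasound, so its sensitivity may be biased upward

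*Combined protocol and SAP*

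**What the plan says.** The confirmation procedure is described under the first of the two Statistical analysis headings. It gives the compression count twice, each time as a minimum: "manual compression of the epigastric region at least three times and evaluation of fluctuation in the tube" in the list of confirmation methods, and "Epigastric compression was performed by applying pressure to the epigastric region at least three times" in the paragraph on technique. Neither place gives a maximum, a stopping rule, or the number of compressions that must show the sign.

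What counts as positive is only described: "the fluctuation of the air and fluid in the stomach inside the esophageal tube can be observed and its sound can be heard". Whether the sign must be seen, heard, or either is not stated. Timing is permissive: "It can be applied from the first inhalation".

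On blinding, the text says "Confirmation was performed single-blind by emergency medicine specialists with at least 5 years of experience, without knowing who performed the procedure and where". The same confirmation also includes lung auscultation and chest inspection, then "auscultation of the epigastric region, placement of capnography, monitoring of water vapor in the tube, manual compression of the epigastric region at least three times". No masking between these signs is described. The ultrasound paragraph does not say whether the ultrasound operator and the reader of the sign were different people, or whether the reader was masked to ultrasound.

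Capnography, by contrast, has a fixed cut-off (above 5 mmHg with a square waveform) and a fixed reading point (after five breaths).

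**The concern.** The compression sign is the subject of the study and one of three index tests for which sensitivity, specificity, likelihood ratios and predictive values are to be calculated against ultrasound. Those measures belong to a test with a defined number of observations and a defined rule for a positive result. This test has neither.

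The two gaps matter more together than apart. If everyone received more compressions under an any-fluctuation rule, sensitivity would rise and specificity would fall, an ordinary trade. If the reader can form a suspicion from the other signs, or from ultrasound, the rule as written lets the reader continue when the oesophagus is suspected and stop at three otherwise. Sensitivity then rises and specificity is largely spared. The bias favours the new sign, and it cannot be removed in analysis unless the results of individual compressions were recorded.

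**Working it through.** **Inputs from the documents.** Minimum of three compressions, no maximum. Groups of 40 successful and 40 failed intubations, less one each for missing data: 40 − 1 = 39 per group. The group sizes are quotas with no power or precision calculation, and no accuracy figure is stated, so there is no plan figure to reproduce.

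**Assumed inputs.** Oesophageal placement is the target condition. Each compression shows fluctuation with probability p = 0.5 in an oesophageal tube and q = 0.02 in a tracheal tube. Any fluctuation counts as positive. The within-patient correlation between compressions, rho, ranges from 0 to 0.9. None of these values is in the documents.

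**Formulas.** With independent compressions, the chance of a positive reading over k compressions is 1 − (1 − p)^k. With correlation, a beta-binomial model is used: a = p(1 − rho)/rho, b = (1 − p)(1 − rho)/rho, and the chance is 1 − B(a, b + k)/B(a, b), where B is the beta function. Specificity is one minus the same quantity with q in place of p.

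At rho = 0, sensitivity is 1 − 0.5^3 = 0.875 at three compressions and 1 − 0.5^6 = 0.984 at six. Specificity is 0.98^3 = 0.941 and 0.98^6 = 0.886.

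| rho | Sensitivity, k = 3 | Sensitivity, k = 6 | Gain | Gain × 39 patients | Specificity, k = 3 | Specificity, k = 6 |
|---|---|---|---|---|---|---|
| 0 | 0.875 | 0.984 | 0.109 | 4.3 | 0.941 | 0.886 |
| 0.3 | 0.763 | 0.873 | 0.110 | 4.3 | 0.956 | 0.935 |
| 0.6 | 0.650 | 0.722 | 0.072 | 2.8 | 0.967 | 0.959 |
| 0.9 | 0.537 | 0.557 | 0.020 | 0.8 | 0.977 | 0.975 |

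**Count that follows suspicion.** Suppose the reader gives six compressions when the oesophagus is suspected and three otherwise, and the suspicion is always right. Sensitivity then comes from the k = 6 column and specificity from the k = 3 column. At rho = 0 this gives 0.984 and 0.941, against 0.875 and 0.941 for a fixed three. Always-correct suspicion makes these upper figures; wrong suspicion reduces the gain and costs some specificity.

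**A sign that shows more readily.** With p = 0.7, the gain from three to six is 0.999 − 0.973 = 0.026 at rho = 0, 0.962 − 0.905 = 0.057 at 0.3, 0.872 − 0.822 = 0.050 at 0.6 and 0.747 − 0.731 = 0.016 at 0.9.

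**Effect of the missing positivity rule.** Take exactly three independent compressions with p = 0.5 and q = 0.02. Any-of-three gives 0.875 sensitivity and 0.941 specificity. Two-or-more gives 3(0.5²)(0.5) + 0.5³ = 0.500 sensitivity and 1 − [3(0.02²)(0.98) + 0.02³] = 0.999 specificity. The choice of rule can matter more than the count.

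**Scale.** The 95% Clopper-Pearson interval is 0.758 to 0.971 for 35/39 and 0.910 to 1.000 for 39/39.

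**The case against.** The strongest reply is that the text only permits variation. No count is reported for any patient, and every patient may have received exactly three. That stands: a reader might infer that the test did vary between patients, and the documents do not show it.

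A reader might also infer that capnography and the other signs were known before compression, because they come first in the list. The documents do not support this. The list is not called a sequence, compression may begin at the first breath, and capnography is read after five. Likewise, the text is silent on masking between signs; it does not say masking was absent. What remains is that the only blinding described covers operator and place ("without knowing who performed the procedure and where").

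A third tempting reading is that false positives climb steeply with more compressions. At an assumed 5% per compression, 1 − 0.95^6 = 26% and 1 − 0.95^10 = 40%. Those figures need prolonged compression of patients with tracheal tubes, the reverse of the behaviour that causes concern here, and they should not be used to size it.

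Compressions by one reader on one stomach are also likely to be correlated. If the sign is nearly all-or-none within a patient, the effect is negligible, and at perfect correlation it is zero. This stands, but the documents give nothing from which to judge the correlation.

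Finally, the modelled shift is small beside the sampling error with 39 per group. That is true, but the confidence interval covers random error only. A bias in one direction is not inside it.

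**Conclusion.** The concern holds in a limited form. The plan does not define one fixed, independently read index test: the number of compressions is open-ended, the positivity rule is missing, and masking to the other signs and to ultrasound is not described. Sensitivity may therefore be biased upward with little loss of specificity.

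Under the assumed rates, an any-positive rule and correct suspicion, the gain from three to six compressions runs from about 2 to 11 points of sensitivity, or roughly 1 to 4 of 39 patients, depending mainly on how far compressions agree within a patient. The direction follows from the rule as written. The size cannot be established from the documents, and whether any bias occurred is unknown. Of the gaps, the missing positivity rule is the most exact defect, because it matters even if every patient received three compressions.

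**What to change.** For the research result only:

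- Score the sign on the first three compressions, which is the protocol's own minimum. Record each as fluctuation yes or no before any further compression.
- Where possible, and without delaying any confirmation step, make that record before the reader knows the ultrasound result.
- Prespecify one positivity rule, including whether the sign must be seen, heard, or either. Tabulate accuracy at one or more, two or more, and three of three.
- State the order in which the signs are read and what the reader is masked to. Fixing the count alone does not stop a suspicion from colouring how a doubtful movement is called.

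Further compressions stay at the clinician's discretion but do not enter the result.

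The cost is a short protocol addition and three tick boxes on the form. The small downside is that a sign appearing only after the third compression counts as negative.

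The documents are written in the past tense, with recruitment running to 30/05/2022. If data were collected without this record, scoring cannot be rebuilt. The report should then give the number of compressions actually given, the positivity rule used, the order of signs and the masking. It should state unrecorded counts and possible upward bias as a limitation on the accuracy estimates.
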